In some villages, several HHs, normally within the extended family, share the same compound. At the selected compound, if there are a number of HHs which could be selected, one HH should be randomly selected from the HHs in the compound (selection should not take the most senior, but be done by numbering the HHs and randomly selecting pieces of papers with the respective numbers written on them).

Selecting households method 1: Village lists

The village list selection of HHs is the preferred selection method. At village level, the village chief or equivalent administrative leader will be approached for a list of all HHs in the village. Team leaders must ensure that this HH list is fully up to date and captures all HHs within the area.

Sampling using the village list is when every *h* HHs in the village are sampled with the initial HH being a random number between 1 and *h*, where *h* is the sampling fraction as detailed below.

The steps to take for sampling using the village list are:

- 1. Find the total number of HHs in the village from the village list
- 2. Calculate the sampling fraction (*h*) using the equation below. Non-whole numbers should be rounded down.

$h = \frac{Total number of households in village}{Number of households to survey}$

- 3. Select the first HH by randomly selecting a number between 1 and *h*. Random number selection can be done in the field by writing numbers on pieces of paper, folding them up, placing them in a container and mixing before drawing one out at random, and then selecting the HH that is on this row in the village list.
- 4. The second HH to sample should be the initial number + *h*.
- 5. Sampling should then proceed in this manner with every h^{th} HH being sampled.

Example of selection of HHs with a village list:

- 1. The protocol is to sample 12 HHs in the village.
- 2. The village list shows that there are 200 HHs in the village.
- 3. Therefore h = 200 / 12 = 16.66, which is rounded down to 16
- 4. The numbers 1 16 are written on pieces of paper, folded up and placed in a container and mixed up. The random piece of paper drawn out is 5.
- 5. The HH on the 5th row of the village list is identified.
- The second HH to select for interviews is 5 + 16 = 21. The HH on the 21st row of the village list is identified.
- Sampling then continues to HHs 37 (= 21 + 16), 53, 69, 85, 101, 117, 133, 149, 165, 181 and 197 giving 12 HHs sampled in total.

Random selection to	Select house	every 16 th (21 = 5 + 16)		
	K			

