House	1 House 21	House 41	House 61	House 81
House	2 House 22	House 42	House 62	House 82
House	3 House 23	House 43	House 63	House 83
Viouse	4 House 24	House 44	House 64	House 84
House	5 House 25	House 45	House 65	House 85
House	6 House 26	House 46	House 66	House 86
House	7 House 27	House 47	House 67	House 87
House	8 House 28	House 48	House 68	House 88
House	9 House 29	House 49	House 69	House 89
House	LO House 30	House 50	House 70	House 90
House	L1 House 31	House 51	House 71	House 91
House	L2 House 32	House 52	House 72	House 92
House	L3 House 33	House 53	House 73	House 93
House	L4 House 34	House 54	House 74	House 94
House	L5 House 35	House 55	House 75	House 95
House	L6 House 36	House 56	House 76	House 96
House	L7 House 37	House 57	House 77	House 97
House	L8 House 38	House 58	House 78	House 98
House	L9 House 39	House 59	House 79	House 99
House	20 House 40	House 60	House 80	House 100

Selecting households method 2: Modified random walk

If there are no village lists available then the HHs can be selected using the Modified Random Walk Procedure. The first HH is determined using the traditional spin the bottle method.

The steps for carrying out a random walk are:

- 1. Identify a central point (i.e. central meeting place, house of the village chief) within the village.
- 2. Spin a bottle/pen at this central point to randomly select a direction. If there is no road in the direction indicated by the bottle, move the bottle clockwise until a road is encountered.
- 3. Count all HHs along the direction indicated by the bottle between the central point and the village boundary. **Do NOT count empty/destroyed houses, businesses, or administrative buildings**. It is important to remember which HHs were included in the counting. A map indicating the HHs and their numbers should be drawn up.
- 4. The sampling fraction *h* should then be calculated using the equation below. Non whole numbers should be rounded down.

 $h = \frac{Total number of households counted}{Number of households to survey}$

- 5. Find the first HH to sample by randomly selecting a number between 1 and *h*. Random number selection can be done in the field by writing numbers on pieces of paper, folding them up, placing them in a container and mixing before drawing one out at random, and then selecting the HH that is on this row in the village list.
- 6. The second HH to sample should be the initial number + h
- 7. Sampling should then proceed in this manner with every h^{th} HH being sampled.

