Example of selection of houses with a random walk (Worrell and Mathieu 2012):

Step 1

- 1. The protocol is to sample 4 HHs to in the village.
- 2. The central point of the village has been found (see diagram below).
- 3. The bottle has been spun and the direction of survey determined.
- 4. A total of 12 HHs have been found between the direction of the bottle and the village boundary (see step 1 in the diagram below).
- 5. Therefore h = 12 / 4 = 3.

Diagram illustrating a random walk with 12 HHs and 4 HHs to be interviewed

Step 2

- 6. The first HH to be surveyed is randomly selected between numbers 1 4 and is number 2. HH number 2 is identified, and is shown with a red star on the diagram above.
- 7. The second HH to sample is HH 2 + 3 = 5. This is shown with a yellow star on the diagram above.
- 8. Sampling then continues to HHs 8 (=5+3) and 11 giving 4 HHs sampled in total.

Obtaining household permission to survey

Once the HH has been selected for interviews, the survey team should approach the house in a friendly and respectful manner and follow the below steps:

- Ask to speak with the head of the HH or the most senior person present.
- Introduce yourself to the head of the HH
- Explain the purpose of your visit and obtain consent from the head of the HH. Ensure the introduction is factual and does not influence or bias the HH's responses

• See below for example introduction:

Hello, my name is <name>. I am here on behalf of the Ministry of Health of <country>, and we are here to conduct a household survey about an activity that has taken place in the village during the past months.

We would like to speak to some members of your households; and if you agree, the survey will only take a few minutes. Your answers will be treated anonymously.

The results will the Ministry of Health improve the programme.

It is your choice to take part, or not to take part, in this survey. If you do not wish to participate, it will not have any consequences for you.

Would you like to take part in our survey?

Answer: **Yes** or **No**.

- If the head of the HH provides consent, ask them to complete the household consent form (appendix C). If the person is not literate, read out the consent form in the local language, and obtain consent by thumb print.
- If the head of the HH **DOES NOT** provide consent for the survey; thank them for their time and continue to the next HH.

What to do if a household cannot be interviewed

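### Both worked examples of household selection in Appendix B are wrong, and the rule leaves open where to stop and what to do when the interval rounds to zero

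*Protocol*

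**What the plan says.** Appendix B of the protocol (the interviewer manual) gives two ways to select households within a village.

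- **Village list (preferred).** Divide the number of households by the number to survey to get h: "Non-whole numbers should be rounded down". Draw a start between 1 and h, then: "Sampling should then proceed in this manner with every h^{th} HH being sampled". No stopping point is given.
- **Modified random walk (when there is no list).** The same rule is applied to the households counted in one spun direction from the central point to the village boundary: "Non whole numbers should be rounded down". The start is again drawn between 1 and h.

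Each method has a worked example.

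- The list example sets "The protocol is to sample 12 HHs in the village" and "The village list shows that there are 200 HHs in the village". It takes h = 16 and start 5, names households 5, 21 and 37, and continues "53, 69, 85, 101, 117, 133, 149, 165, 181 and 197 giving 12 HHs sampled in total".
- The walk example has 12 households, a target of 4 and h = 3. It then says: "The first HH to be surveyed is randomly selected between numbers 1 4 and is number 2". A dash has probably been lost between the 1 and the 4 in the text extraction; the upper limit of 4 is clear.

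The manual's operational target is 20 households per village. The main text, under the heading on the number of villages and households, gives 15.

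**The concern.** The protocol relies on random selection of households, and team leaders carry it out on site from this manual. The examples are what a team leader will copy, and both disagree with the rule they illustrate.

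The miscount matters because it hides a gap in the rule. Rounding down means the interval does not, in general, divide the list exactly, so a team must either stop at the target or go on to the end. The example's count points to stopping; its list of household numbers points to going on. The two readings have different consequences. One leaves some households with no chance of selection, which weighting cannot repair. The other gives a variable number of households per village, whereas Appendix D, on selection of primary sampling units, reasons from the same number being interviewed in each.

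The manual also says nothing about a list or walk that holds fewer households than the target.

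**Working it through.** **Inputs**, all from Appendix B unless stated: list example N = 200, n = 12, start 5; walk example N = 12, n = 4; operational target n = 20 (15 in the main text). The protocol gives no village sizes, so every other N below is an illustrative assumption.

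**1. The list example.** h = floor(200/12) = floor(16.67) = 16, as stated. The number selected from start s, running to the end of the list, is floor((N − s)/h) + 1. For s = 5 this is floor(195/16) + 1 = 12 + 1 = 13. Direct listing agrees: 5, 21, 37, 53, 69, 85, 101, 117, 133, 149, 165, 181, 197 is 13 households. The stated 12 is not reproduced; the 12th household is 181.

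Over all starts, 200 = 12 × 16 + 8, so starts 1 to 8 give 13 households and starts 9 to 16 give 12.

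**2. If teams stop at the target.** The furthest household that can be reached is n × h. Households beyond it, N − n × floor(N/n) of them, have no chance. In the example, 12 × 16 = 192, so households 193 to 200 are unreachable: 8/200 = 4%.

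**3. If teams run to the end.** Every household belongs to exactly one of the h possible samples, so each has chance 1/h. Selection is equal-probability and the take is never below n, but it varies.

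| Target n | Assumed N | h | Unreachable if stopped at n | Take if run to end |
|---|---|---|---|---|
| 20 | 39 | 1 | 19 (49%) | 39 |
| 20 | 59 | 2 | 19 (32%) | 29–30 |
| 20 | 100 | 5 | 0 | 20 |
| 20 | 150 | 7 | 10 (6.7%) | 21–22 |
| 20 | 199 | 9 | 19 (9.5%) | 22–23 |
| 20 | 200 | 10 | 0 | 20 |
| 15 | 29 | 1 | 14 (48%) | 29 |
| 15 | 100 | 6 | 10 (10%) | 16–17 |
| 15 | 200 | 13 | 5 (2.5%) | 15–16 |

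The rows N = 29, 39, 59 and 199 sit one below a multiple of the target, which is the worst case for their interval.

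**4. The walk example.** h = 12/4 = 3, so the rule allows starts 1, 2 and 3. These give {1, 4, 7, 10}, {2, 5, 8, 11} and {3, 6, 9, 12}: four households each, and chance 1/3 for all. The example also allows start 4, which gives {4, 7, 10}, only three households. With four equally likely starts, households 4, 7 and 10 appear under two of them (2/4 = 0.50) and the other nine under one (1/4 = 0.25).

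**5. Interval of zero.** floor(19/20) = 0 and floor(14/15) = 0. Any list or walk with fewer households than the target gives h = 0, and no start can be drawn. This is more likely on the walk, because only one direction is counted while the divisor is the whole village target.

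**6. Circular alternative.** Draw the start from 1 to N, step by h, wrap to the top and stop at n. Because n × h ≤ N, the n households are distinct. Each household is reached from exactly n of the N starts, so its chance is n/N.

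**The case against.** The strongest reply is that the written steps never tell teams to stop at the target, and the list example runs on to 197, a household that stopping at 12 would exclude. Read that way, every household has chance 1/h and there is no selection bias, only some extra interviews. A footnote in Appendix B already contemplates raising the number of households per village. This stands as far as it goes. It does not settle the matter, because the same example claims to have hit its target of 12, so a team could fairly take either reading.

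The walk slip is confined to the illustration. The governing step says 1 to h, the start actually drawn (2) is valid and yields four households, and the walk is only the fallback. That limits the harm, but the example still teaches a range that contradicts the rule.

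A reader might infer that the survey systematically leaves out households at the edge of villages and so misstates coverage. The documents do not support this. It needs teams to stop at the target, lists ordered by location, and coverage that differs at the end of the list. The first is only one reading, and nothing describes how village lists are ordered. On a walk, the last households counted are those furthest from the centre, but the point about stopping still applies.

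The large percentages are likewise not estimates for Malawi. At the only list size the document mentions, the illustrative 200, the unreachable share is 0% for a target of 20 and 2.5% for 15.

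**Conclusion.** The point holds as a defect in the selection instructions. Three facts rest on the document alone: the list example names 13 households and calls them 12; the walk example draws its start from 1 to 4 when its own rule gives 1 to 3; and the rule fails when there are fewer households than the target.

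The consequence of the missing stopping point is conditional. If teams stop, N − n × floor(N/n) households are unreachable: 4% in the example and, at a target of 20, anything from 0% (N = 200) to 49% (N = 39), depending on village sizes that the protocol does not give. If teams run on, selection stays equal-probability and the cost is a variable, sometimes larger, take. Bias in the coverage estimate is possible but not shown. No sample-size figure depends on the miscount. Severity is moderate.

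**What to change.** Choose one rule and state it.

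- **Preferred: circular systematic sampling.** Draw the start from 1 to N, step by h, continue from the top of the list when the end is reached, and stop at exactly the target. Every household then has chance n/N and the take is fixed. On the walk, N is the number of households counted in the spun direction.
- **Simpler: state that sampling runs to the end of the list.** This keeps equal chances but accepts a take above target in some villages.

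Then:

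1. Correct the list example to match: 13 households ending at 197 if run to the end, or 12 ending at 181 if circular with start 5.
2. Correct the walk example. If the start rule stays at 1 to h, the range becomes 1 to 3. If circular sampling is adopted for the walk, the range is 1 to the number counted, with wrapping shown.
3. Add a rule for short counts. If fewer households than the target are counted along the walk, take all of them and spin again for the remainder. If the whole village list is shorter than the target, take every household.

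The cost is a few lines in the interviewer manual and the household-selection training exercise. Circular sampling needs no extra staff or visits; running to the end adds interviews in villages whose size is not a multiple of the target.

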Survey Objective (SO) 1. To measure validated treatment coverage of PZQ and ALB in SAC, and adults relative to coverage targets

SO 2. To compare reported and validated coverage of PZQ and ALB for SAC and adults

SO 3. To assess coverage in SAC and adults disaggregated by gender

SO 4. To assess coverage in SAC disaggregated by school attendance

SO 5. Collect information on why targeted eligible individuals did not receive or accept treatment

- SO 6. To assess the impact of radio campaigns on improving knowledge about schistosomiasis
- SO 7. To assess whether radio campaigns improved attendance/coverage of treatment with PZQ and ALB

Where validated coverage rate is defined as:

Total number of interviewed individuals that ingested the target drug Total number of interviewed individuals * 100 %

Note that people interviewed but with missing information on whether they ingested the drug will be assumed to have **not** taken the drug for the purposes of calculating validated coverage.

Study Design

Overview

The coverage survey will take place in nine implementation units (IUs) known as the district. Each IU will be considered separately. Within each IU, the survey will be household (HH) based in randomly selected villages. See Appendix D for a detailed explanation of the statistical approach to the coverage survey.

Survey team

Interviewers must not have been involved in any previous activities related to the NTD programme, specifically the MDA, to ensure that they remain unbiased.

Selection of enumerators will be done by the Programme Managers, ensuring that none of the interviewers were involved with the MDA in July 2017. The majority of interviewers have experience in coverage surveys, but everyone will attend compulsory training to ensure standardisation of knowledge and ability to carry out coverage surveys. Training will include teaching about schistosomiasis and soil transmitted helminth infections as well as familiarisation with the health questionnaires and the phones that the information will be stored on.

Although programme managers will not take part in any of the individual interviews in interviewee households, they will facilitate in the training and logistics of the survey as well as support the teams of enumerators if problems arise.

See Appendix A for more details of the survey teams and logistics.

Timing of survey

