Mchinji	Surveyed Previously	
Rumphi	Surveyed Previously	
Ntcheu	Not surveyed previously	
Dedza	Not surveyed previously	Yes
Chitipa	Not surveyed previously	

Number of villages and households to survey within each IU

Sample size calculations indicated that 17 villages per IU, and 15 HHs per village are required to obtain 9% precision on the coverage of SAC and adults within each district. As the MDA was community-wide, two adults will be randomly sampled, and to capture more information about school attendance rates, all eligible children within a HH will be interviewed. See Appendix D for full details of sample size calculations.

Selection of villages to survey within each IU

A list of all traditional areas (TAs), and all their villages, within the selected districts were collected from the district health offices. The list of all TAs and their villages will ensure all villages have the opportunity to be selected. Each village was allocated a number and was then randomly selected by the in-country team using a random number generator until 18 villages per district were selected. The sample size calculation requires 17 villages, for logistical purposes 18 villages have been selected so that each team will visit 6 villages per district.

A short list of 'reserve villages' was provided, such that if a selected village cannot be visited for security or other unpredictable reasons, it can be replaced with another in the same district. See Appendix B: Coverage Survey Interviewer Manual for more details. Appendix E has a list of all selected villages and reserves

Selection of households to survey within each village

HH selection will be performed on site. Selection will be random, with the methodology dependent on whether HHs lists are available (see data collection protocol). If lists are not available HH selection will by the modified random walk procedure (please see data collection protocol).

Although ideally the survey would include nomadic populations and transient communities, because this is a HH-based survey, those without a fixed residence at the site selected for the coverage survey will not be included in the survey target population.

Selection of individuals to survey within each household

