If people in the selected home refuse to participate, try to encourage participation. If they still refuse, indicate this on the survey form, and count this HH as one of the HHs visited, indicate this on the survey form. **DO NOT replace the house with another HH**.

If no-one is at home in the selected HH, return later in the day. If, again, nobody is at home, indicate this on the survey form in the "Household questions" section, and count this HH as one of the HHs visited. **DO NOT** replace the HH with another one⁵.

If there are no eligible individuals for interview in the HH (e.g. no SAC live at the address, or all HH members moved in after the drug distribution), note this on the survey form, do not ask the questions, **but replace the HH with the next HH in the direction of travel with any eligible interviewee.**

Selecting individuals within a household

- If the head of the HH agrees to participate, proceed with the interview.
- Two adults and all school-aged children (SAC) within each HH will be randomly selected for interview.
- SAC is all children aged 5 -14 years
- Adults is all people aged 15 or over

The steps to take for interviewing SAC within a HH are:

- 1. Write the name of each SAC (i.e. all children aged 5 -14) in the HH on a separate piece of paper. Include all SAC living in the HH, even if they are not in the HH at the time.
- 2. Begin interviewing the children who are available for interview

⁵ If this happens for many households (e.g. frequently >2 households/village) in several villages, the supervisors should discuss with the study co-ordinator to consider increasing the number of households to randomly select per village.

3. If a selected individual cannot be interviewed, record who they are and please see below.

The steps to take for interviewing adults within a HH are:

- Write the name of each adult (i.e. all individuals 15 or over) in the HH on a separate piece of paper.
 Include all adults living in the HH, even if they are not in the HH at the time.
- 2. Fold up the pieces of paper and put into a container
- 3. Pick out two pieces of paper
- 4. Interview the adults whose names are on the paper
- 5. If a selected individual cannot be interviewed, please see below

What to do if an individual cannot be interviewed

- If an individual (SAC or adult) cannot be interviewed then return later to try to interview them.

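### The example in the household replacement rule contradicts the rule and the protocol's own adult eligibility, so teams may drop adult-only households from the adult coverage sample

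*Protocol*

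**What the plan says.** The rule is in Protocol, Appendix B, under What to do if a household cannot be interviewed. It begins "If there are no eligible individuals for interview in the HH (e.g. no SAC live at the address", adds as a second example that all members moved in after the distribution, and says to note this, ask none of the questions, "but replace the HH with the next HH in the direction of travel with any eligible interviewee".

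The next part of Appendix B, Selecting individuals within a household, says "Two adults and all school-aged children (SAC) within each HH will be randomly selected for interview" and "Adults is all people aged 15 or over". Neither sentence requires a child in the household.

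The main text agrees. Survey Objective (SO) 1 is "To measure validated treatment coverage of PZQ and ALB in SAC, and adults relative to coverage targets", and SO 2 and SO 3 also cover adults. Under Number of villages and households to survey within each IU, the protocol says "As the MDA was community-wide, two adults will be randomly sampled", and the 9% precision stated there is for SAC and adults alike.

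Two other places narrow adult eligibility. Details of the MDA in Malawi 2017 limits adult treatment to high-risk areas. Appendix D, Sampling of individuals within a HH, gives the standard practice as two adults provided they are eligible for treatment.

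**The concern.** The two examples test different things. Everyone having moved in after the distribution is a test of the whole household. Having no SAC is a test of the children only. It would suit a survey of children alone, but this survey also samples adults.

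A team that acts on the example skips a household in which it could have interviewed two adults. Adults who do not live with a child aged 5-14 then have no chance of selection, and adult coverage under SO 1 to SO 3 describes only adults living with school-age children. For SO 2 that group would be compared with reported community figures that count all registered people aged 15 and over.

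A confidence interval does not show an exclusion of this kind, and a larger sample does not reduce it. Later adjustment would be difficult, because the questions are not asked in a replaced household, so its adult counts would probably not be recorded.

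**Working it through.** **1. The plan's own sample size, reproduced.** Inputs from Appendix D: coverage 50%, margin 9 points, 95% confidence, intra-class correlation 0.1, 24 individuals per village, 2 children per household, 20% non-response.

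- Simple random sample: 1.96² × 0.25 / 0.09² = 118.56
- Design effect: 1 + (24 − 1) × 0.1 = 3.3
- Individuals: 118.56 × 3.3 = 391.3 (plan: 391)
- Villages: 391.3 / 24 = 16.3, rounded up to 17
- Households per village: 24 / (2 × 0.8) = 15

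The arithmetic holds. The problem is who can enter the adult sample.

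**2. The texts side by side.**

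| Text | Adult-only household |
|---|---|
| Condition: no eligible individual | Kept, since adults are eligible |
| Example: no SAC at the address | Replaced |
| Replacement must hold any eligible interviewee | Would itself qualify as a replacement |
| Two adults drawn per household, adults being 15 or over | Kept |

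The example is the only one of the four that removes the household.

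**3. Size of the effect where the example is followed.** Let q be the share of adults living in SAC-free households and D the coverage of adults living with SAC minus that of adults living without.

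- True adult coverage = (1 − q) × C(with) + q × C(without)
- The survey estimates C(with)
- Bias = C(with) − true coverage = q × D

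The documents give neither q nor D. Assumed values, in percentage points:

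| q | D = 0 | D = ±10 | D = ±20 |
|---|---|---|---|
| 15% | 0 | ±1.5 | ±3.0 |
| 30% | 0 | ±3.0 | ±6.0 |

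Wider assumptions (q 10-40%, D 5-30 points in absolute value) give 0.5 to 12 points. The planned half-width is 9 points. If only some teams follow the example, the bias lies between zero and q × D, and part of it appears as a difference between teams.

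**4. Effect on SAC precision if adult-only households are kept and not replaced.** Half-width = 1.96 × √(0.25 × DEFF / n), with m = households × SAC per household × 0.8, DEFF = 1 + (m − 1) × 0.1 and n = 18 × m for the 18 villages selected. The 1.6 and 1.2 SAC per household are assumptions; they correspond to 20% and 40% of households without SAC if the others average 2.

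| Households per village | SAC per household | m | DEFF | n | Half-width (points) |
|---|---|---|---|---|---|
| 15 | 2.0 | 24.0 | 3.30 | 432 | ±8.57 |
| 15 | 1.6 | 19.2 | 2.82 | 345.6 | ±8.85 |
| 15 | 1.2 | 14.4 | 2.34 | 259.2 | ±9.31 |
| 20 | 1.6 | 25.6 | 3.46 | 460.8 | ±8.49 |
| 20 | 1.2 | 19.2 | 2.82 | 345.6 | ±8.85 |

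The 20-household rows are shown because Appendix B, Selecting households to interview, sets 20 per village, whereas the main text sets 15.

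**The case against.** **The governing words keep adult-only households.** The trigger is the absence of any eligible individual, and the example is only a parenthesis. This stands. A reader might infer that the protocol deliberately excludes adult-only households, and the documents do not support that: a careful team could keep them. What remains is an explicit field example that points the other way, with six teams left to resolve the conflict.

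**The example fits part of the survey area.** Where adults were not targeted, a household without SAC has nobody eligible for treatment, and item 14 of the village questionnaire asks whether the treatment included adults. This also stands for such villages. But the main text and Appendix B sample adults without that condition, and nothing limits the example to those villages.

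**The direction of bias is unsupported.** A reader might infer that adult coverage is overstated, because adults with schoolchildren would hear of the campaign through school. Nothing in the protocol compares adults living with and without SAC. Adults in high-risk areas were to be reached by community treatment, and radio and social mobilisation were used as well. The direction is open.

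**The SAC cost may be smaller than shown.** The plan's 2 children per household is stated as an average and may already include households with none. This survey also interviews all SAC in a household, which may raise the yield. Both points stand.

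**Conclusion.** The example contradicts both the rule it illustrates and the protocol's eligibility for adults. Where teams act on it, adults not living with a child aged 5-14 are excluded, and adult coverage under SO 1 to SO 3 refers to a narrower group than stated. How many teams would do so cannot be known from the document.

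The bias is q × D. It is 1.5 to 6 points in absolute value under the assumed 15-30% of adults and 10-20 point difference, zero if coverage does not differ, and of either sign. These figures illustrate the scale; they are not estimates from the protocol. The SAC coverage estimate does not suffer this exclusion, and the sample size calculation is unaffected.

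This is more than a matter of wording, because it can change the population behind a stated objective without leaving a trace in the interval.

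**What to change.** - Replace the example in Appendix B so that it describes a household where no SAC and no adult eligible for the survey lives at the address.
- Where adults are part of the survey population, keep adult-only households, interview up to two adults and record zero SAC. The household form already counts boys and girls separately, so zero can be entered.
- Reconcile the passages that sample adults in every household (main text on numbers of villages and households; Appendix B on selecting individuals) with those that restrict adults to high-risk areas or to those eligible for treatment (Details of the MDA in Malawi 2017; Appendix D). Teams need to know in which villages adults count as eligible.

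The edit is a sentence or two in the manual. The cost is fewer SAC interviews: a half-width of about ±8.85 to ±9.3 points at 18 villages and 15 households, against ±8.57 with no loss of SAC. It is about ±8.5 to ±8.85 if 20 households are visited, and smaller again if interviewing all SAC raises the yield. Adding a further household for SAC interviews only is not needed, and would give that next household the extra selection probability that replacement creates.
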